#### **9.4.1.2. Analysis of Secondary Endpoints**

Secondary endpoints will be analyzed on the ITT population.

##### **Changes in Intrahepatic Immune Response**

Variation in proportion of major cell populations, such as but not limited to CD45+ T-cells, CD4+ T-cells, CD8+ T-cells, Natural Killer cells, and dendritic cells, defined by single cell

transcriptomics (in FNABs) and immunofluorescence staining (in core needle biopsies), will be assessed at Week 40 and compared to baseline, overall and by study panel.

The functional characterization of major cell populations will be assessed by transcriptomics and/or proteomics for major cell populations of interest at Week 40 and compared to baseline similarly.

### **Changes in Intrahepatic Viral Nucleic Acids and Proteins**

Changes from baseline in cccDNA level and/or transcriptional activity will be assessed using the general considerations outlined above.

Furthermore, the difference in the level of infected hepatocytes at baseline will be assessed by comparing cccDNA level and/or transcriptional activity.

Analyses of other viral markers will be performed descriptively. Statistical analyses will depend on the assay technology applied and the scope of the analyses.

#### **9.4.1.3. Analysis of Exploratory Endpoints**

Exploratory endpoints will be analyzed on the ITT population.

The association between intrahepatic markers and blood (immune and viral) markers will be explored both at baseline and on-treatment by study panel using graphical displays and relevant correlation coefficients.

Impact of baseline characteristics on selected efficacy variables and their association with intrahepatic and blood markers will also be evaluated using similar methods.

Identification of markers (either intrahepatic or blood) that could potentially be associated with selected efficacy variables (such as decrease in blood HBsAg levels, intrahepatic cccDNA levels or any other relevant variables) will be conducted. Impact of treatment on different blood and hepatic markers will also be evaluated.

#### **9.4.2. Safety Analyses**

All safety analyses will be made on the Safety Population (Section 9.3).

Safety will be evaluated by means of descriptive summaries of AEs including AEs of special interest to any of the study interventions, clinical laboratory tests, ECGs, vital signs, and physical examinations. The safety analysis will be done by study phase. Results will be presented in tabular format and/or graphically over time, as appropriate.

#### **Adverse Events**

The verbatim terms used in the CRF by investigators to identify AEs will be coded using the Medical Dictionary for Regulatory Activities (MedDRA). Intervention-emergent AEs are AEs with onset during the intervention phase or that are a consequence of a pre-existing condition that has worsened since baseline. All reported intervention-emergent AEs will be included in the

analysis. For each AE, the percentage of participants who experience at least 1 occurrence of the given event will be summarized.

Summaries, listings, datasets, or participant narratives may be provided, as appropriate, for those participants who die, who discontinue intervention due to an AE, or who experience a severe or a serious AE.

#### *Adverse Events Related to the Applied Study Procedures*

Summaries, listings, datasets, or participant narratives will be provided, as appropriate, for those enrolled participants who die, or who experience an AE or a severe or a serious AE related to the applied study procedures.

All AE's linked to the study procedure will be evaluated in conjunction with other systemic symptoms and laboratory abnormalities: information on time of onset, duration of events, time to resolution, concomitant therapies, and relationship to study procedures (eg, liver biopsies, blood collection and leukapheresis) will be summarized and described in the report.

#### **Clinical Laboratory Tests**

Laboratory data will be summarized by type of laboratory test. Descriptive statistics will be calculated for each laboratory analyte at baseline and for observed values and changes from baseline at each scheduled time point by study phase. A graphical presentation of changes from baseline over time in selected laboratory tests will be also used.

The laboratory abnormalities will be determined according to the criteria specified in the DAIDS Toxicity Grading Scale (see Section 10.9, Appendix 9, DAIDS Table) or in accordance with the normal ranges of the clinical laboratory if no gradings are available. The number and percentage of the participants who experience (worst) laboratory abnormalities will be tabulated by intervention arm and study phase. Shifts in toxicity grades will be tabulated by study phase.

#### **Electrocardiogram**

Electrocardiogram data will be summarized by ECG parameter. Descriptive statistics will be calculated at baseline and for observed values and changes from baseline at each scheduled time point. Frequency tabulations of the abnormalities will be made.

The ECG variables that will be analyzed are heart rate, PR interval, QRS interval, QT interval, and QTcF.

Descriptive statistics of QTc intervals and changes from baseline will be summarized at each scheduled time point. The percentage of participants with QTc interval >450 milliseconds, >480 milliseconds, or >500 milliseconds will be summarized, as will the percentage of participants with QTc interval increases from baseline >30 milliseconds or >60 milliseconds. Shifts in QTc interval categories will be tabulated by study phase.

All clinically relevant abnormalities in ECG waveform that are changes from the baseline readings will be reported (eg, changes in T-wave morphology or the occurrence of U-waves).

## **Vital Signs**

Vital signs including temperature, pulse rate, and supine blood pressure (SBP and DBP) will be summarized over time, using descriptive statistics and/or graphically. The percentage of participants with values beyond clinically important limits will be summarized.

## **Physical Examinations**

Physical examination findings will be summarized at each scheduled time point. Descriptive statistics will be calculated at baseline and for observed values and changes from baseline at each scheduled time point. Frequency tabulations of the abnormalities will be made.

### **9.4.3. Other Analyses**

#### **Pharmacokinetic Analyses**

Descriptive statistics (number of participants, mean, SD, coefficient of variation, geometric mean, median, minimum, and maximum) will be calculated for the plasma concentrations of JNJ-3976, JNJ-3924, and optionally, JNJ-6379, NA and/or PegIFN- $\alpha$ 2a, as applicable, and for the derived plasma PK parameters (noncompartmental analysis).

Special attention will be paid to the plasma concentrations and PK parameters of those participants who discontinued the study for an AE, or who experienced an AE  $\geq$ Grade 3 or an SAE.

For each participant with intensive PK sampling, plasma concentration-time data of JNJ-3976, JNJ-3924, and/or JNJ-6379, and/or NA and/or PegIFN- $\alpha$ 2a will be graphically presented. Similarly, graphs of the mean plasma concentration-time profiles and overlay graphs with combined individual plasma concentration time profiles will be produced. Pharmacokinetic parameters will be subjected to an exploratory graphical analysis, including various transformations, to get a general overview.

Population PK analysis of plasma concentration-time data of JNJ-3976, JNJ-3924, and optionally, JNJ-6379, NA and/or PegIFN- $\alpha$ 2a may be performed using nonlinear mixed-effects modeling. Data may be combined with those from Phase 1 and/or 2 studies to support a relevant structural model. Available baseline characteristics (eg, demographics, laboratory variables, genotypes) may be included in the model as necessary. Details will be given in a population PK analysis plan and results of the population PK analysis, if applied, will be presented in a separate report.

Individual estimates of PK parameters may be generated from the population PK analysis for potential use in exposure-response analysis.

## Pharmacokinetic/Pharmacodynamic Analyses

Relationships of PK parameters for JNJ-3976, JNJ-3924, and optionally, JNJ-6379, NA and/or PegIFN- $\alpha$ 2a with selected efficacy and with selected safety endpoints may be evaluated and graphically displayed.

Modeling of key PD parameters (eg, HBsAg, HBV DNA) may be performed using population PK/PD. If PK/PD modeling of key efficacy endpoints is performed, treatment effect and possible covariates such as disease progression may be investigated. Other biomarkers may be explored at the sponsor's discretion.

## Resistance Analysis

The results of HBV viral sequencing will be evaluated by the sponsor virologist. Relevant changes in amino acid and/or nucleic acid variations (eg, substitutions) in the HBV genome will be tabulated and described.

Additional exploratory characterization of the HBV viral sequence and phenotype may be performed and reported separately.

## Pharmacogenomic Analysis

The statistical approach for analyzing the exploratory host DNA research, including epigenetic analyses, may depend on the objective of the analyses (efficacy, safety, and PK) and possibly relevant genes at the time of analysis. Analyses will be conducted at the sponsor's discretion, will always be under the sponsor's supervision, and results will be presented either in the clinical study report or a separate report.

## Host Exploratory Biomarker Analysis

Statistical approaches to explore correlations between treatment response/clinical outcome and blood and liver biomarkers vary and depend on the different data types of the applied technology platforms, as well as on the extent of observed differences between participants. Analyses will be conducted at the sponsor's discretion, will always be under the sponsor's supervision, and results will be presented either in the clinical study report or a separate report.

## 9.5. Interim Analysis

Two IAs may be performed: when all participants have completed Week 20 in the intervention phase (or discontinued earlier) and when they have completed Week 72 in the follow-up phase (ie, Follow-up Week 24) (or discontinued earlier). These IAs will be performed by the sponsor to support interactions with health authorities, as well as to support internal decisions about additional studies and/or investigation of other combination regimens.

Both primary and interim analyses will be based on all data available at the predefined cut-off time points and may include data at later time points for those participants who have reached subsequent visits.

**9.6. Independent Flare Expert Panel**

An IFLEP will be appointed for this study. The IFLEP is composed of 3 independent medical experts with experience and expertise in hepatitis B and its treatment. The IFLEP will monitor ALT flares and will make recommendations regarding flare management based on an analysis of aggregate data.

In order to allow for an unbiased assessment, members of the committee will not serve as study investigators.

Further details on the IFLEP process will be included in the IFLEP charter.

## 10. SUPPORTING DOCUMENTATION AND OPERATIONAL CONSIDERATIONS

### 10.1. Appendix 1: Abbreviations and Definitions of Terms

AE	adverse event
AFP	alpha-fetoprotein
ALP	alkaline phosphatase
ALT	alanine aminotransferase
AST	aspartate aminotransferase
AUC	area under the plasma concentration-time curve
AUC 0-xh	area under the plasma concentration-time curve from administration to x h
AUC 0-last	area under the plasma concentration-time curve from administration to last quantifiable sampling point
AUC τ	area under the plasma concentration-time curve over the dose interval (tau) at steady-state
AUC ∞	area under the plasma concentration-time curve to last sampling point from time zero extrapolated to infinity
bpm	beats per minute
CAM	capsid assembly modulator
cccDNA	covalently closed circular deoxyribonucleic acid
CKD-EPI	Chronic Kidney Disease Epidemiology Collaboration
CL/F	total apparent oral clearance
C max	maximum plasma concentration
CRF	case report form
CT	computed tomography
CYP	cytochrome P450
DAIDS	Division of Acquired Immunodeficiency Syndrome
DBP	diastolic blood pressure
DDI	drug-drug interaction
DNA	deoxyribonucleic acid
EASL	European Association for the Study of the Liver
ECG	electrocardiogram
eDC	electronic data capture
EFD	embryofetal development
eGFR	estimated glomerular filtration rate
eGFR cr	estimated glomerular filtration rate based on serum creatinine
ELISpot	enzyme-linked immunospot
EOS	end of study
EOSI	end of study intervention
ETV	entecavir
FNAB	fine needle aspiration biopsy
FSH	Follicle-stimulating hormone
FU Wx	Follow-up Week x
GCP	Good Clinical Practice
GLP	Good Laboratory Practice
HBc	hepatitis B core protein
HBcrAg	hepatitis B core-related antigen
HBe	hepatitis B e
HBeAg	hepatitis B e antigen
HBs	hepatitis B surface
HBsAg	hepatitis B surface antigen
HBV	hepatitis B virus
HCC	hepatocellular carcinoma
HCV	hepatitis C virus
HDV	hepatitis D virus
HEV	hepatitis E virus
HIV-1(-2)	human immunodeficiency virus type 1 (type 2)
HLA	human leukocyte antigen
HRT	hormonal replacement therapy

IA	interim analysis
IB	Investigator's Brochure
ICF	informed consent form
ICH	International Council for Harmonisation of Technical Requirements for Pharmaceuticals for Human Use
ICMJE	International Committee of Medical Journal Editors
ICS	intracellular cytokine staining
IEC	Independent Ethics Committee
IFLEP	Independent Flare Expert Panel
IFN	interferon
IFN- $\gamma$	gamma interferon
IgM	immunoglobulin M
IL	interleukin
INR	International Normalized Ratio
IRB	Institutional Review Board
ISR	injection site reaction
ITT	Intent-to-treat
IU/mL	International Units Per Milliliter
IWRS	interactive web response system
LLN	lower limit of normal
LLOQ	lower limit of quantification
MoA	mode of action
MRI	magnetic resonance imaging
NA	nucleos(t)ide analog
NOAEL	no observed adverse effect level
(q)PCR	(quantitative) polymerase chain reaction
PD	pharmacodynamic(s)
PegIFN- $\alpha$ 2a	pegylated interferon alpha-2a
PK	pharmacokinetic(s)
PBMC	peripheral blood mononuclear cell
pgRNA	pre-genomic ribonucleic acid
PQC	Product Quality Complaint
Q4W	once every 4 weeks
qd	once daily
QTcF	QT interval corrected for heart rate according to Fridericia
RBC	red blood cell
RNA	ribonucleic acid
RNAi	ribonucleic acid interference
SAE	serious adverse event
SBP	systolic blood pressure
SC	subcutaneous
SD	standard deviation
siRNA	small interfering RNA
SUSAR	suspected unexpected serious adverse reaction
$t_{1/2\text{term}}$	terminal half-life
T4	thyroxine
$t_{\max}$	time to reach the maximum plasma concentration
TAF	tenofovir alafenamide
TEAE	treatment-emergent adverse event
TNF	tumor necrosis factor
TSH	thyroid-stimulating hormone
ULN	upper limit of normal
WBC	white blood cell

**Definitions of Terms**

Study intervention	Prior to Protocol Amendment 5: JNJ-73763989 (JNJ-3989), JNJ-56136379 (JNJ-6379) and NA (either ETV, tenofovir disoproxil, or TAF) As of Protocol Amendment 5: JNJ-73763989 (JNJ-3989) and NA (either ETV, tenofovir disoproxil, or TAF)
Functional cure	HBsAg seroclearance 24 weeks after end of treatment
HBsAg or HBeAg seroclearance	HBsAg or HBeAg negativity, respectively, based on the assay used
HBsAg or HBeAg seroconversion	HBsAg or HBeAg negativity and anti-HBs or anti-HBe antibody positivity, respectively
Virologic breakthrough	Confirmed on-treatment HBV DNA increase by $>1 \log_{10}$ IU/mL from nadir or confirmed on-treatment HBV DNA level $>200$ IU/mL in participants who had HBV DNA level $<\text{LLOQ}$ of the HBV DNA assay
ALT/AST nadir	Lowest ALT/AST value during study participation

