As of Protocol Amendment 5: The term “study intervention” throughout the protocol, refers to JNJ-3989, NA, and optional PegIFN  $\alpha$ 2a.

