6. Participants must have HBsAg  $>100$  IU/mL at screening.
7. Participants must have a body mass index (weight in kg divided by the square of height in meters) between 18.0 and 35.0 kg/m^2, extremes included.
8. Participants must have fibroscan liver stiffness measurement  $\leq 9.0$  kPa within 6 months prior to screening or at the time of screening.

**Note:** Other radiologic liver staging modalities (eg, acoustic radiation force impulse) might be used if standard practice at the site or if otherwise validated and agreed with the

sponsor. Results should be equivalent to Metavir F0-F2 with absence of signs of portal hypertension.

**Note:** Conventional imaging procedures (eg, conventional liver ultrasound, computed tomography [CT] or magnetic resonance imaging [MRI]) and serum marker panels are not allowed to rule out severe fibrosis or cirrhosis.

9. Female participants of childbearing potential must have a negative highly sensitive serum pregnancy test ( $\beta$ -human chorionic gonadotropin [ $\beta$ -hCG]) at screening and a negative urine pregnancy test on Day 1 before the first dose of study intervention.
10. Criterion modified per Amendment 5

10.1 A woman must be (as defined in Section 10.8, Appendix 8, Contraceptive and Barrier Guidance and Collection of Pregnancy Information):

- a. not of childbearing potential
- b. of childbearing potential and practicing a highly effective, preferably user-independent method of contraception (failure rate of <1% per year when used consistently and correctly) for at least 30 days prior to screening and agrees to remain on a highly effective method while receiving study intervention and until 90 days after last dose of study intervention.

Examples of highly effective methods of contraception are located in Section 10.8, Appendix 8, Contraceptive and Barrier Guidance and Collection of Pregnancy Information.

**Note:** Typical use failure rates may differ from those when used consistently and correctly. Use should be consistent with local regulations regarding the use of contraceptive methods for participants in clinical studies.

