**Note (no longer applicable as of Protocol Amendment 5, because of the removal of JNJ-6379 as study intervention):** Female participants of childbearing potential who are on a stable treatment regimen with hormonal contraceptives (ie, same dose and not starting or stopping hormonal contraceptive use for at least 30 days prior to screening) should continue the same dose regimen until 90 days after the last dose of study intervention. Ethinylestradiol-containing contraceptives are only allowed if the ethinylestradiol content is  $\leq 20$   $\mu$ g. Female participants stable on an ethinylestradiol-containing regimen with a dose  $> 20$   $\mu$ g who switch to an ethinylestradiol-containing regimen with a dose  $\leq 20$   $\mu$ g, should be on that new regimen for at least 1 week before the first dose of study intervention. For female participants of childbearing potential who will start a hormonal contraceptive treatment during the study, ethinylestradiol-containing contraceptives are not allowed.

11. Male participants must agree to wear a condom when engaging in any activity that allows for passage of ejaculate to another person during the study intervention period and until 90 days after last dose of study intervention.

12. Female participants must agree not to donate eggs (ova, oocytes) for the purposes of assisted reproduction during the study intervention period and until 90 days after last dose of study intervention.
13. Male participants must agree not to donate sperm for the purpose of reproduction during the study intervention phase and until 90 days after last dose of study intervention.
14. Participants must sign an ICF indicating that he or she understands the purpose of, and procedures required for, the study and is willing to participate in the study.
15. Participants must separately consent if he or she agrees to undergo optional study procedures (ie, leukapheresis, intensive PK, and/or optional biopsy). Refusal to give consent to one or all of these optional study procedures does not exclude from participation in the study.
16. In the investigator's opinion, the participant is able to understand and comply with protocol requirements, instructions, and study restrictions and is likely to complete the procedures as planned for this study.

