\* In countries where TAF is available, it will be one of the NA treatment options.

\*\* For PegIFN- $\alpha$ 2a, dose adjustment may be applicable for participants who develop laboratory abnormalities during PegIFN- $\alpha$ 2a treatment (refer to Section 6.6).

\*\*\* May vary based on local regulations.

\*\*\*\* Participants enrolled before Protocol Amendment 5 was in effect, may have received JNJ-6379 as part of their study intervention. As of Protocol Amendment 5: study intervention includes JNJ-3989, NA and optionally PegIFN  $\alpha$ 2a

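### Appendix 1 leaves optional PegIFN-α2a out of *study intervention*, so on that reading the 90-day contraception and donation rules can lapse during a 24-week PegIFN course

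*Protocol*

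**What the plan says.** Four places in the protocol count PegIFN-α2a as study intervention. The synopsis (Section 1.1) says that as of Amendment 5 the term "throughout the protocol, refers to JNJ-3989, NA, and optional PegIFN"-α2a, and Section 2 repeats this. The footnotes to both tables of interventions (synopsis and Section 6.1) agree; the one in Section 6.1 reads "As of Protocol Amendment 5: study intervention includes JNJ-3989, NA and optionally PegIFN". The SAP is in line: its Study Design section (1.2) lists PegIFN under study treatment, and its Functional Cure section (5.4.2.5) counts PegIFN among the study interventions that must have stopped.

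The Definitions of Terms in Appendix 1 (Section 10.1) differ: "As of Protocol Amendment 5: JNJ-73763989 (JNJ-3989) and NA (either ETV, tenofovir disoproxil, or TAF"). PegIFN does not appear there.

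Four inclusion criteria in Section 5.1 depend on the term:

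- 10.1, female contraception: the participant "agrees to remain on a highly effective method while receiving study intervention and until 90 days after last dose of study intervention".
- 11: "Male participants must agree to wear a condom when engaging in any activity that allows for passage of ejaculate to another person", with the same 90-day end point.
- 12: "Female participants must agree not to donate eggs (ova, oocytes) for the purposes of assisted reproduction during the study intervention period and until" the same 90-day limit.
- 13, on sperm donation, has its own 90-day limit, counted like the others: "until 90 days after last dose of study intervention".

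None of the four names PegIFN, so the definition alone settles when they end.

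**The concern.** The protocol allows PegIFN to be the last drug still being given. JNJ-3989 is last injected at Week 44. NA stops at Week 48 if the Week 44 laboratory criteria are met. PegIFN starts after the Week 40 biopsy and before the Week 48 visit, and runs for 12 or 24 weeks at the investigator's choice.

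For such a participant the two definitions start the 90-day clock from different drugs. One starts it at the last NA dose, the other at the last PegIFN injection. A site that looks the term up in the glossary could release a participant from contraception, condom and donation duties while weekly PegIFN injections continue. Section 7.1 makes pregnancy a reason to stop JNJ-3989 and/or PegIFN, so the protocol does not treat pregnancy during PegIFN as immaterial. At stake is a reproductive-safety window. No endpoint or analysis is touched.

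**Working it through.** **Inputs.** From the schedules of activities (Sections 1.3.1 and 1.3.3): Week 40 = Day 281, with a biopsy window of ± 4 weeks; Week 44 = Day 309; Week 48 = Day 337; end of PegIFN at Day 85 or 169 counted from its start. From Section 4.1: last JNJ-3989 injection at Week 44. From Section 6.6.1: NA stops at Week 48 if the criteria are met. From Section 5.1: 90 days after the last dose.

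**Reproducing the plan's day numbers.** Day = 7 × week + 1. Weeks 40, 44 and 48 give 281, 309 and 337; PegIFN weeks 12 and 24 give 85 and 169. All match.

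**Expiry on the Appendix 1 reading, NA stopped at Week 48.** The last NA dose (Day 337) is later than the last JNJ-3989 dose (Day 309), so expiry = 337 + 90 = Day 427, about Week 61.

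**24-week PegIFN.** Last injection = start + 7 × 23 = start + 161. It falls after Day 427 when start > 427 − 161 = 266. Injections after expiry are those with start + 7k > 427, for k = 0 to 23.

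| PegIFN start | Last injection | Days past Day 427 | Injections after Day 427 | Expiry if PegIFN counts (last injection + 90) |
|---|---|---|---|---|
| Day 254 (day after earliest permitted biopsy, 281 − 28 = 253) | 415 | −12 | 0 | 505 |
| Day 266 | 427 | 0 | 0 | 517 |
| Day 282 (day after on-time biopsy) | 443 | 16 | 3 | 533 |
| Day 302 (three weeks after on-time biopsy) | 463 | 36 | 6 | 553 |
| Day 330 (Week 47) | 491 | 64 | 10 | 581 |
| Day 336 (day before Week 48) | 497 | 70 | 10 | 587 |

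For starts from Day 282 to Day 336 the two readings differ by 533 − 427 = 106 days up to 587 − 427 = 160 days.

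**12-week PegIFN.** Last injection = start + 7 × 11 = start + 77; the latest is 336 + 77 = Day 413. That is before Day 427, so nothing lapses during dosing. Cover after the last injection is 427 − 413 = 14 days at the shortest, against 90 if PegIFN counts. For a Day 282 start it is 427 − 359 = 68 days.

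**NA continued through PegIFN.** The last NA dose is then no earlier than the last PegIFN injection, so expiry is at least 90 days after that injection on either reading. There is no lapse.

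**The case against.** The strongest reply is that the protocol has already settled the meaning. Two definitions say they apply throughout the protocol, both intervention tables class PegIFN as investigational, and Sections 6.1 and 7.1 treat it as study intervention. The glossary entry's half for the period before Amendment 5 also omits PegIFN, although a synopsis footnote says it joined at Amendment 4. That looks like an entry not updated when PegIFN was added. This is probably how the omission arose, and a careful reader would include PegIFN. But the entry is worded for Amendment 5, and a definitions page is where a site looks up a term, so the conflict remains in current text.

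Mitigations also exist. Exclusions 23 and 24 bar planned pregnancy or fathering for as long as the participant is enrolled, urine pregnancy tests continue at least every 4 weeks in follow-up, and PegIFN has its own consent form, which was not available for review and may carry its own instructions. These address intention, detection and information. They do not replace the contraception, condom and donation criteria.

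Three stronger readings are tempting but not supported:

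- A reader might infer that serious adverse event reporting also depends on the definition, through the 30-day phrase in Section 8.5.1. That section already requires all events to be reported until the last study-related procedure. A 24-week course started before Week 48 ends before Week 72, with follow-up still running to Follow-up Week 48. For anyone remaining in follow-up the 30-day phrase does not bind.
- A reader might infer that at least 6 injections always fall outside the window. That assumes a start about three weeks after the biopsy. A start the day after an on-time biopsy gives 3, and a start by Day 266 gives none.
- A reader might infer that every PegIFN recipient is exposed. A 12-week course, or continued NA, removes the lapse during dosing.

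**Conclusion.** The contradiction is real and stands in current text. Its consequence is narrow. On the Appendix 1 wording, criteria 10.1, 11, 12 and 13 expire on Day 427 while PegIFN is still being injected if three conditions hold together: a 24-week course, a start after Day 266, and NA stopped at Week 48 and not restarted. The overrun is then 3 to 10 injections (16 to 70 days) for starts between Day 282 and Day 336. After a 12-week course the only effect is shorter cover following the last injection, 14 days at the least.

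The figures assume on-schedule weekly injections and a last NA dose on Day 337; the ± 3 day visit window at Week 48 would move expiry to between Day 424 and Day 430. The documents do not say how many of the roughly 24 participants in Panels 1 and 2 would meet all three conditions. Because following one page as written lets a safety rule lapse during dosing, this is more than a clerical slip and should be corrected. It does not bear on safety reporting or on the statistical analysis.

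**What to change.** Reconcile the *study intervention* entry in Appendix 1 with the synopsis, Section 2 and the intervention-table footnotes, so that the protocol carries one definition. Then confirm that criteria 10.1, 11, 12 and 13 read as intended for participants who receive PegIFN, including those who stop NA at Week 48. Which drug the 90 days should run from, and for how long, is for the clinical team and is not proposed here. The cost is about one line of protocol text and a check of four criteria. The SAP needs no change.
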